MCMC	Markov Chain Monte Carlo
MedDRA	Medical Dictionary for Regulatory Activities
POEM	Patient-Oriented Eczema Measure
PP	per protocol
SAE	serious adverse event
SAP	statistical analysis plan
TBSA	total body surface area
TEAE	treatment-emergent adverse event
US	United States
UV	ultraviolet

5 Introduction

Atopic dermatitis (AD) is a very common chronic dermatosis with a prevalence of 10% to 20% in children and 1% to 3% in adults [1]; AD poses difficult therapeutic challenges and may have a profound effect on a patient's quality of life. The disease gives rise to itching and severely dry skin, and is characterized by an allergic predisposition, pruritus, erythema, oozing, crusting, excoriations, lichenification, sensitivity to allergens/irritants, and a susceptibility to secondary infections [2, 3].

Reactive treatment with topical corticosteroids is the classical paradigm of care, but while these compounds are effective, they are restricted in long-term use by local and systemic side effects. Specifically, the use of topical corticosteroids is associated with potential local and systemic side effects including skin atrophy, telangiectasia, dyspigmentation, suppression of the hypothalamic-pituitary-adrenal axis and the rebound effect. Aside from corticosteroids, there is only a limited armament of topical treatments available for AD, most of which have certain side effects that limit their use.

Ascomycin derivatives, such as pimecrolimus, represent a class of anti-inflammatory macrolactams that inhibit the phosphatase calcineurin [4-6]. Studies on the effect of ascomycin derivatives and other immunophilin ligands in animal models of skin inflammation provided evidence that they are effective in the treatment of skin diseases in humans such as chronic plaque psoriasis, without the well-known side effects of topical corticosteroids [7, 8]. Intensive studies on structure-activity relationships and comparative pharmacological evaluations resulted in the discovery and development of pimecrolimus [9, 10]. Pimecrolimus selectively acts on cells involved in skin inflammation, targeting T cells and mast cells, and inhibiting the production and release of proinflammatory cytokines.

ELIDEL® (pimecrolimus) Cream, 1% was approved by the Food and Drug Administration (FDA) in 2001 as second-line therapy for the short-term and noncontinuous chronic treatment of mild to moderate AD in nonimmunocompromized adults and children 2 years of age and older who fail to respond adequately to, or are advised against using, other topical prescription treatments. ELIDEL Cream is an innovative therapeutic agent with a mode of action different from topical corticosteroids; the product is generally safe and has been shown to be effective in the treatment of AD.

In order to improve patient satisfaction with use, the sponsor is developing a new formulation of pimecrolimus. This formulation will include the same concentration of the active ingredient as ELIDEL Cream (pimecrolimus 1%), but in a lotion form. It is expected that the safety profile of this new formulation, IDP-124 Lotion, will be similar to that of ELIDEL Cream. Additionally, the sponsor proposes to evaluate IDP-124 Lotion in patients with

moderate to severe AD in order to establish the safety and efficacy of the product for use in patients for whom there is no approved alternative. In this way, IDP-124 Lotion will enhance and extend the available therapeutic options for patients with AD.

The current clinical study is designed to evaluate the efficacy, safety, and tolerability of IDP-124 Lotion for the treatment of moderate to severe AD in pediatric and adult subjects.

6 Study Objectives and Purpose

The objectives of this study are to evaluate the efficacy, safety, and tolerability of IDP-124 Lotion for the treatment of moderate to severe AD in pediatric and adult subjects.

7 Investigational Plan

7.1 Investigators and Study Administrative Structure

Approximately 20 investigational centers are planned to participate in this study. Each clinical investigator will be required to provide a copy of his/her curriculum vitae and medical license, complete a financial disclosure statement, and generate a list of study personnel who will be involved in the study, with a summary of their roles and qualifications.

7.2 Summary of Study Design

This is a multicenter, randomized, double-blind, parallel group, vehicle-controlled study to evaluate treatment success using a 5-point Investigator Global Assessment (IGA) scale from clear to severe; the Eczema Area Severity Index (EASI); improvement in total affected body surface area (TBSA); assessment of pruritus (itching) and sleep disturbance; Patient-Oriented Eczema Measure (POEM) from subjects and parents/legal guardians of pediatric subjects, and investigator's assessment for presence or absence of signs and symptoms of AD.

Approximately 348 subjects, ages 2 and older, are planned for randomization (232 subjects to IDP-124 Lotion and 116 subjects to IDP-124 Vehicle Lotion). The study consists of a 6-week double-blind treatment period and 4-week, post-treatment follow-up. Study visits include Screening, Baseline, and Weeks 1, 2, 4, 6, and 10 (subjects will return to the clinic at Week 10 for a post-treatment follow-up visit).

At the Screening Visit, subjects or their parents/legal guardians (when applicable) will sign an informed consent/assent form, provide their medical histories, report their previous and concomitant medications, and be evaluated against the inclusion/exclusion criteria. Premenses females (ages 9 and older) and all females of childbearing potential will have urine pregnancy tests performed. An abbreviated physical examination will be performed, vital signs measured (sitting blood pressure, respiration, pulse, and temperature), and blood and urine specimens will be collected for serum chemistry, hematology, urinalysis evaluations

and serum pregnancy for pre-menses females (9 and older) and FOCBP. During this visit, the investigator will perform the IGA, evaluate the subject for TBSA affected by AD, and for the other signs and symptoms of AD.

At the Baseline Visit, prior to being evaluated by the investigator and study staff, subjects or parents/legal guardians (if applicable) are to complete the POEM. At this visit, medical histories and concomitant medication use will be updated, and the inclusion/exclusion criteria will be confirmed. Adverse events since the Screening Visit will be assessed, and all premenses females (9 and older) and FOCBP will have urine pregnancy tests performed. During the Baseline Visit, the IGA, EASI, pruritus and sleep disturbance, and subject's assessment of AD will be completed, and the investigator will assess TBSA affected by AD and evaluate the subject for other signs and symptoms of AD.

After confirming eligibility at the Baseline Visit, subjects will be randomized in a 2:1 ratio to receive either IDP-124 Lotion or IDP-124 Vehicle Lotion. Subjects or parents/legal guardians of pediatric subjects will apply the first dose of the assigned study drug to the affected areas of the skin at the investigational center under the supervision of designated study personnel. Subjects will receive the study drug and given verbal and written instructions for treatment application. Specifically, the subjects will be instructed to apply the lotion to the affected areas twice daily, at approximately the same time each day, about 12 hours apart. The subjects will also receive diaries, with instructions to complete a record of all applications (of study drug and bland emollient use) and to note any missed applications of the study drug.

Throughout the study, safety will be assessed by reviewing the occurrence of adverse events (AEs), assessing vital sign measurements and abbreviated physical examination findings (conducted at Baseline and Week 6), and noting any additions or changes in concomitant medication/therapies uses. Blood and urine samples will be collected at Screening and Week 6 visits for routine safety laboratory evaluations and serum pregnancy testing, as applicable, and urine pregnancy tests will be obtained for all pre-menses females (9 and older) and FOCBP at each study visit (except Week 1). Efficacy assessments of the IGA, EASI, Pruritus and Sleep Disturbances, TBSA affected by AD, evaluation for signs and symptoms of AD, and Subject Assessment, will be performed throughout the study. In addition, the POEM (Appendix 17.3) will be completed by the subjects/parents/legal guardians at Baseline, Week 6 and Week 10.

Additionally, at selected sites, standardized photography will be performed on subjects who provide photographic consent, at Baseline, Weeks 2, 4, 6, and 10.

The study design and schedule of assessments is presented in Table 1.

Table 1: Study Design and Schedule of Assessments

	Pre-Treatment		7	Treatment Perio	d		Post- treatment
Visit	1	2	3 a	4 a	5 a	6 a	7 a
Week PROCEDURES	Screening Day -35 to 0	Baseline Day 1	Week 1 ± 2 days	Week 2 ± 2 days	Week 4 ± 3 days	Week 6 -3/+5 days	Week 10 ± 5 days
Obtain informed consent/assent	X						
Review medical history	X	X^{b}					
Review inclusion/exclusion criteria	X	X^{b}					
Review previous therapies	X	X^{b}					
Conduct urine pregnancy test (all pre-menses females [9 and older] and FOCBP) ^c	X	X		X	X	X	X
Conduct abbreviated physical examination ^d	X					X	
Obtain vital signs ^e	X					X	
Collect blood and urine samples for hematology, serum chemistry, and urinalysis (including serum pregnancy) ^f	X					Xg	
Evaluation of TBSA	X	X^{h}	X	X	X	X	X
Perform IGA	X	X^{h}	X	X	X	X	X
Photographs (select sites only) ⁱ		X		X	X	X	X
Assess other signs and symptoms of AD (hyper/hypopigmentation, dry skin)		X^h	X	X	X	X	X
Perform EASI assessment		X^{h}	X	X	X	X	X
Assess pruritus and sleep disturbance ^j		X^{h}	X	X	X	X	X
Subject's assessment of AD		X^{h}	X	X	X	X	X
POEM for adult subjects or parents of pediatric subjects ^k		X ^h				X	X
Randomize qualified subjects via IRT		X					
Review dosing instructions (Appendix 17.1)		X	X	X	X		
Dispense study drug		X		X	X		

	Pre-Treatment		1	reatment Perio	od		Post- treatment
Visit	1	2	3 a	4 a	5 a	6 a	7 a
Week PROCEDURES	Screening Day -35 to 0	Baseline Day 1	Week 1 ± 2 days	Week 2 ± 2 days	Week 4 ± 3 days	Week 6 -3/+5 days	Week 10 ± 5 days
Weigh study drug		X	X	X	X	X	
Dispense subject diary		X	X	X	X	X ^l	
Application of (one of two doses of) study drug in clinic		X	X	X	X		
Apply study drug ^m		•					
Collect study drug				X	X	X	
Collect/review subject diary			X	X	X	X	X
Review concomitant medications / therapies		X	X	X	X	X	X
Review adverse events		X	X	X	X	X	X
Exit study							X

Abbreviations: CBC/Diff = complete blood count/differential; EASI = Eczema Area Severity Index; IGA = Investigator's Global Assessment; POEM = Patient-Oriented Eczema Measure; TBSA = total body surface area

- a Post-baseline Visits 3-6 are to be scheduled in reference to Visit 2 (Baseline Visit) and within the designated window for each visit. Visit 7 (4-week post-treatment visit) is to be scheduled 4 weeks following Visit 6 and within the designated window.
- b Confirmation of evaluations conducted at the Screening Visit.
- c For pre-menses females (9 and older) and FOCBP, the urine pregnancy test must be completed at all scheduled visits, as per schedule. Serum pregnancy testing will be completed at Screening and Week 6 only. Subjects with a positive pregnancy test at any time during the study will be discontinued.
- d The abbreviated physical examination at the Screening and Week 6 Visits includes height and weight.
- e Vital sign measurements include temperature, pulse, respirations, and sitting blood pressure.
- f Refer to Appendix 17.5 for a list of analytes that will be analyzed for the blood and urine sample collections.
- g Any clinically significant laboratory abnormality present at Week 6 (or Early Termination) is to be followed to resolution or until clinically stable as determined by the investigator.
- h Perform assessment prior to study drug application or application of any other approved products on the affected areas.
- i For select sites performed photography, include target lesion and full-front/back images (reference photography manual).
- Pruritus and sleep disturbance to be collected based on a 24 hour window prior to assessment.
- k The POEM is to be completed by the subject or subject's parent/legal guardian prior to the subject being seen by the investigator or study staff.
- A different subject diary will be dispensed at Week 6 to track blank emollient use only (i.e., IP use will not be tracked after end of treatment/Week 6).
- m On study visit days, subjects will apply their one of the two doses of study drug at the investigational site (i.e., if study visit is in the morning, they will not apply prior to coming in for their study visit). Subject will apply last dose of study drug on the day prior to Week 6 visit.

8 Selection and Withdrawal of Subjects

8.1 Subject Inclusion Criteria

Subjects meeting all of the following criteria will be eligible for study entry:

- 1. Male or female at least 2 years of age and older.
- 2. Written and verbal informed consent must be obtained; subjects less than age of consent must sign an assent (as required per IRB/IEC guidelines) for the study and a parent or a legal guardian must sign the informed consent (if subject reaches age of consent during the study they should be re-consented at the next study visit).
- 3. Nonimmunocompromized male or female who failed to respond adequately to other topical prescription treatment for AD or for whom those treatments are not advisable.
- 4. Clear diagnosis of AD fulfilling the diagnostic criteria of Hanifin and Rajka¹³ that affects ≥ 5% of TBSA (see Appendix 17.4 for full list of diagnostic criteria to reference); subject should have had a diagnosis of AD for at least 3 months; i.e., determined by subject-reported or parent-reported duration of subject experiencing itchy and dry skin for 3 months or longer (at Screening and Baseline visits).
- 5. Subject must have a score of 3 (moderate) or 4 (severe) on the IGA scale at the Screening and Baseline visits.
- 6. Subjects must be willing to comply with study instructions and return to the clinic for required visits; subjects under the age of consent must be accompanied by the parent or legal guardian at the time of assent/consent signing.

8.2 Subject Exclusion Criteria

Subjects meeting any one of the following criteria will be excluded from the study:

1. Females who are pregnant, breast feeding, or who wish to become pregnant during the study period. Women of childbearing potential and females that are premenses (9 and older) must be willing to practice effective contraception for the duration of the study. (Effective contraception is defined as stabilized on oral contraceptive for at least 3 months, IUD, condom with spermicidal, diaphragm

¹ Pre-menses females and FOCBP include any female who has not undergone successful surgical sterilization (hysterectomy, bilateral tubal ligation or bilateral oophorectomy) or is not postmenopausal (defined as amenorrhea > 12 consecutive months; or women on hormone replacement therapy with documented plasma follicle-stimulating hormone level > 35mLU/mL). Even women who are using oral, implanted, or injectable contraceptive hormones, an intrauterine device, barrier methods (diaphragm, condoms, spermicidal) to prevent pregnancy, practicing abstinence or where partner is sterile (e.g., vasectomy), should be considered to be of child bearing potential.

² Urine pregnancy tests must have a minimum sensitivity of 25mIU HCG/mL of urine and must be performed within 72 hours prior to the start of study drug. Kits will be provided by the CRO/designee.

with spermicidal, implant, Nuvaring, injection, transdermal patch or abstinence.) Females on birth control must have taken the same type for at least three months prior to entering the study and must not change type during the study. Those who have used any hormonal contraception in the past must have discontinued usage at least three months prior to the start of the study.

- 2. Active cutaneous bacterial or viral infection in any treatment area at Baseline (e.g., clinically infected AD).
- 3. Sunburn, extensive scarring, extensive tattoo, or pigmented lesion(s) in any treatment area at Baseline, which would interfere with evaluations.
- 4. History of confounding skin conditions (e.g., psoriasis, rosacea, erythroderma, or ichthyosis, other than ichthyosis vulgaris).
- 5. History or presence of:
 - a. Basal/squamous cell carcinoma of skin and/or melanoma treated within the past 2 years
 - b. carcinoma of cervix effectively treated less than 5 years ago
 - c. immunological deficiencies or diseases, HIV, or serious recurrent infection
 - d. clinically significant severe renal insufficiency or severe hepatic disorders
- 6. Current serious infection (including any skin infection).
- 7. Failure to respond to topical pimecrolimus/tacrolimus.
- 8. Use within 1 month prior to Baseline and/or expected use during the study:
 - a. oral or injectable corticosteroids
 - b. ultraviolet (UV) A/UVB therapy
 - c. psoralen plus UVA therapy
 - d. tanning booths
 - e. nonprescription UV light sources
 - f. systemic immunomodulators (except biologics, see #14(a)) or immunosuppressive therapies
 - g. interferon
 - h. cytotoxic drugs
 - i. oral tacrolimus
- 9. Use within 14 days prior to Baseline and/or expected use during the study (in the affected area(s)):
 - a. medicated topical products (e.g., containing urea, salicylic acid, ammonium lactate)
 - b. topical antibiotics
 - c. calcipotriene or other vitamin D preparations (stable dose of Vitamin D use is allowed)
 - d. topical retinoids

- e. topical antihistamines
- f. topical corticosteroids (other than hydrocortisone, see #12)
- g. nonsteroidal topical prescription products for atopic dermatitis (e.g., Eucrisa)
- h. other topical prescription products
 - inhalation steroids and/or systemic antihistamines are allowed, as long as subjects are on stable dose for at least 2 weeks before Baseline
- 10. Subjects who are on an unstable dose of opioids, or who plan to start using opioids during the course of the study (stable dose is allowed, as long as it remains unchanged during the course of the study).
- 11. Use of systemic/oral antibiotics within 14 days of Baseline visit (oral antibiotics are permitted during the study [postbaseline]).
- 12. Use of 1% hydrocortisone cream within 3 days prior to Baseline and/or expected use during the study (in the affected area(s)).
- 13. Use of any nonmedicated topical product (e.g., sunscreens, lotions, creams, bland emollients) the morning of the Baseline.
- 14. Has received systemic treatment for the skin, including but not limited to:
 - a. For existing or new biologic agents (e.g., Stelara, Dupixent), should not be used within at least 3 months prior to baseline.
 - b. Oral psoriasis medications (e.g., Otezla) should be considered systemic therapies and should not be used within at least 4 weeks prior to baseline.
- 15. Has received treatment with any investigational drug or device within 60 days or 5 drug half-lives (whichever is longer) prior to the Baseline Visit, or is concurrently participating in another clinical study with an investigational drug or device
- 16. Subjects with a known hypersensitivity to pimecrolimus or any other ingredients in the study medication.
- 17. Subjects who are not willing to minimize or avoid excessive natural and artificial sunlight exposure during treatment.
- 18. Subjects who are unable to communicate or cooperate with the investigator due to language problems, poor mental development, or impaired cerebral function.
- 19. Subjects with any underlying disease that the investigator deems uncontrolled, or poses a concern for the subjects safety while participating in the study.
- 20. Subjects who have a planned surgical or medical procedure that will overlap with participation in the study.

8.3 Subject Withdrawal Criteria

When possible, subjects who discontinue from the study prior to completing the 6-week treatment period should return to the clinical center to perform the assessments scheduled for

the ET visit. If appropriate, discontinued subjects may be placed on other conventional therapy upon request or whenever clinically necessary, as determined by the physician. The End of Study source documents and all relevant data should be entered into the electronic case report form (eCRF) system at the time the subject discontinues from the study.

Reasons for subject withdrawal may include, but are not limited to, the following:

- Progression of AD, as determined by the investigator, which requires treatment with a prohibited therapy
- At the investigator's discretion for safety reasons (e.g., severe adverse reactions or unauthorized concomitant therapy)
- Subject withdrawal
- When the requirements of the protocol are not followed
- When a concomitant therapy likely to interfere with the results of the study is reported or required by the subject (the investigator will report all such information on the source documents/eCRFs and decide, in accordance with the sponsor, whether the subject is to be withdrawn)
- When a subject is lost to follow-up; the investigator (or designee) will try twice to reach the subject by telephone, email and/or text message, and will send a follow-up letter by certified mail before considering the subject as lost to follow-up. These actions will be documented on the End of Study source documents, and a copy of the follow-up letter maintained in the investigator's file
- If a subject becomes pregnant during the treatment period, the study drug will be discontinued immediately, the subject will be discontinued from the study, and the investigator will notify the sponsor. The pregnancy will be followed to term with the outcome reported to the sponsor.

9 Treatment Plan

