- 11. For select sites only: At Visits 4, 5, and 6 (Weeks 2, 4, and 6) only obtain representative photos of the affected area(s). Please refer to the photography manual for details.
- 12. At Visits 4, and 5 (Weeks 2 and 4) only: Obtain assigned kit using IRT and dispense both tubes of study drug from the assigned kit, weigh the tubes (with the cap on) individually, to the nearest tenth of a gram, and complete the drug accountability log. New tubes of study drug will **not** be dispensed at Visit 3 (Week 1) or Visit 6 (Week 6).
- 13. At Visit 3 (Week 1) only, re-dispense the two tubes (dispensed at Baseline) and a new diary to the subject and/or their parent/legal guardian. Review the dosing instructions with the subject and/or parent/legal guardian.
- 14. Remind the subject to refrain from applying the study drug and any allowed non-medicated topical products (e.g., sunscreens, lotions, creams, bland emollients) the morning of the next study visit.

15. At Visit 6 (Week 6) only:

- a. Prior to conducting any evaluations, instruct the subject or their parent/legal guardian to complete the appropriate POEM.
- b. Obtain vital sign measurements.
- c. Measure height and weight.
- d. Conduct an abbreviated physical examination (excluding urogenital/reproductive systems).
- e. After all AD assessments, collect blood and urine samples for routine safety laboratory analysis (hematology, serum chemistry, urinalysis, and serum pregnancy for pre-menses females (9 and older) and FOCBP). Process and ship the samples to the central safety laboratory per instructions provided in the study-specific laboratory manual.
- f. Instruct the subject to continue use of bland emollient (if applicable) between Week 6 and Week 10 (post-treatment phase). Dispense new subject diary with bland emollient use application only.
- g. If this is the ET Visit, record the reason for subject discontinuation from the study in the source document. All other subjects should be scheduled to return for Visit 7 (Week 10 [± 5 days])/ Post-Treatment Follow-Up Visit.

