12.8.1 Analysis Populations

Approximately 348 subjects with moderate or severe atopic dermatitis (defined as an IGA score of 3 or 4) will be enrolled and randomized in the study. With a 2:1 randomization ratio, it is anticipated that:

- Approximately 232 subjects will be randomized to receive IDP-124 Lotion
- Approximately 116 subjects will be randomized to receive IDP-124 Vehicle Lotion

Efficacy analyses will be performed using the ITT population, the Week 6 PP population, and the Week 10 PP population. The ITT analysis set will be considered primary for the evaluation of efficacy. Safety analyses will be performed using the safety population during the treatment period (Baseline to Week 6), and during the post treatment period (Week 6 to Week 10).

All subjects who are randomized and dispensed study drug will be included in the ITT population.

All subjects who are randomized and receive at least 1 confirmed dose of study drug will be included in the safety population.

All subjects in the ITT population who complete the Week 6 visit without any major protocol violations will be included in the Week 6 PP population. The Week 6 PP population will include subjects in the ITT population who did not meet any of the following criteria:

- Violated the inclusion/exclusion criteria
- Used an interfering concomitant medication prior to Week 6
- Did not attend the Week 6 visit
- Missed more than 1 post-baseline study visit prior to Week 6

- Have not been compliant with the dosing regimen (i.e., subjects must apply 80% 120% of the expected applications of study medication during participation in the study)
- Out of visit window at the Week 6 visit by more than \pm 5 days

Subjects that discontinue from the study due to an adverse event related to study treatment or documented lack of treatment effect (and/or worsening of condition) will be included in the Week 6 PP population.

All subjects in the Week 6 PP population who complete the Week 10 visit without any major protocol violations will be included in the Week 10 PP population. Specifically, the Week 10 PP population will include subjects in the Week 6 PP population who did not meet any of the following criteria:

- Used an interfering concomitant medication between Week 6 and Week 10
- Did not attend the Week 10 visit
- Out of visit window at the Week 10 visit by more than \pm 5 days

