12.8.2 Sample Size Determination

The following power calculations were computed using the IGA efficacy results from the Pimecrolimus Lotion, 1% (Elidel) NDA 21-302. Considerations were given the change in expected entry level severity of the current study. Nquery Advisor Version 7.0 with the Fisher's exact test option was used to calculate the power using a 2-sided test with an alpha of 0.05. The following table presents the efficacy estimates used in this power calculation.

Percent Dichotomized IGA Success* for Treatment Groups

	Pimecrolimus Lotion, 1%	Vehicle
Percent	23.6%	6.3%
Success		

* Success was defined as at least a 2-grade improvement from Baseline in the IGA score and an IGA score equating to "Clear" or "Almost Clear".

Overall, 232 IDP-124 Lotion treated subjects and 116 vehicle lotion treated subjects will have greater than 95% power to detect a statistically significant outcome for a 2-sided test with an alpha level of 0.05.

It was noted that the estimates extracted from the above studies are based on the LOCF method of handling missing values while the proposed Phase 3 analysis will account for missing values using multiple imputations. The power stated above sufficiently exceeds 95% which will compensate for the difference in handling of missing data.

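### No efficacy assessment is planned after early exit, so the Week 6 IGA of early leavers kept in the ITT set rests on an imputation that ignores stopping drug

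*Combined protocol and SAP*

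**What the plan says.** Section 8.3 covers early stopping in terms of leaving the study. Where possible, "subjects who discontinue from the study prior to completing the 6-week treatment period should return to the clinical center" for the ET assessments, and the end-of-study data are entered when the subject leaves. The possible reasons include some where the subject may still be willing to attend, for example "When the requirements of the protocol are not followed".

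Section 11.1.3 merges the ET visit with Visit 6, so IGA and EASI are due at exit. Item 15g then says: "If this is the ET Visit, record the reason for subject discontinuation from the study in the source document". Only the other subjects are scheduled for Week 10. The Synopsis (Safety) follows early leavers for four weeks, for adverse events only.

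Section 12.8.1 defines the primary efficacy set: "All subjects who are randomized and dispensed study drug will be included in the ITT population". It also keeps subjects who leave for a related adverse event or lack of effect in the per-protocol sets.

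Section 12.8.3 fills missing values by MCMC multiple imputation, run separately in each arm on the scores at Baseline and Weeks 1, 2, 4, 6 and 10. It states that the method does not depend on data being missing at random. Section 12.5.5 adds LOCF, a repeated-measures GEE on observed data, and a tipping point analysis with no further detail.

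**The concern.** The primary endpoint is IGA success at a fixed time, Week 6, in everyone randomized and dispensed drug. For a subject who exits at Week 2 or 3, no visit is planned at which that outcome could be seen, even if the subject would come. Nothing in the imputation marks the subject as having stopped drug, so post-exit scores are projected along patterns supplied mainly by subjects who stayed on treatment. If the drug effect fades after stopping, active leavers are credited with effect they no longer have. An outcome that could often be observed is replaced by an assumption, inside the primary analysis.

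The text on missing data makes this harder to see. Standard MCMC imputation is valid under missing at random given the variables in the model. Running it by arm does not remove that requirement.

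**Working it through.** **1. What happens to an early leaver.**
- At exit: an ET visit with IGA, if it takes place (8.3, 11.1.3).
- After exit: four weeks of adverse event follow-up (Synopsis). For exits at Week 2 or later this reaches Week 6 (2 + 4 = 6), yet no IGA is asked for.
- At Week 6 and Week 10: no scheduled efficacy assessment.
- In the analysis: retained in ITT (12.8.1) and imputed (12.8.3).
- The ET score itself: no stated role. The imputation uses only scheduled-visit scores. Section 11.1.5 places off-window scheduled visits on the scheduled-visit form but does not say whether ET visits are included. An ET IGA could therefore be read as Week 6, assigned to another visit, or left out.

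**2. The plan's own power figure.** Inputs from Section 12.8.2: success 23.6% active and 6.3% vehicle; 232 and 116 subjects; two-sided alpha 0.05; Fisher's exact test. The claim is that "232 IDP-124 Lotion treated subjects and 116 vehicle lotion treated subjects will have greater than 95% power". Summing the two binomial probabilities over all outcomes with Fisher p ≤ 0.05 gives 99.27%, and the normal approximation gives 99.28%. The claim reproduces.

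**3. Illustration of bias in the active arm.** The documents give no dropout rate, so a stopping share d of 5% to 20% is assumed. Assume also that active leavers are imputed at 23.6% but would truly succeed at 6.3%, and that vehicle leavers succeed at 6.3% and are imputed at that rate.

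Overstatement = d × (23.6 − 6.3) = d × 17.3 points.

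| d | Active leavers (232 × d) | Overstatement (points) | True difference (points) | Fisher power at true rates |
|---|---|---|---|---|
| 5% | 12 | 0.9 | 16.4 | 98.8% |
| 10% | 23 | 1.7 | 15.6 | 98.0% |
| 15% | 35 | 2.6 | 14.7 | 96.9% |
| 20% | 46 | 3.5 | 13.8 | 95.2% |

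**4. Effect of stopping in both arms.** Suppose instead that every leaver truly fails and is imputed at the arm's rate. With stopping shares dA (active) and dV (vehicle), the difference is overstated by dA × 23.6 − dV × 6.3 points.
- 10% and 10%: 2.36 − 0.63 = 1.73; true difference 15.6, power 98.5%.
- 20% active, 10% vehicle: 4.72 − 0.63 = 4.09; true difference 13.2, power 94.7%.
- 10% active, 20% vehicle: 2.36 − 1.26 = 1.10; true difference 16.2, power 99.2%.

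Vehicle stopping offsets part of the bias here. The net size depends on both rates and on what leavers do afterwards.

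**The case against.** A reader might infer that stopping the lotion always means leaving the study, and that the Week 6 outcome is lost in all who stop. The documents do not support that. Only pregnancy expressly ties stopping drug to study exit. The list in 8.3 is permissive, and for interfering therapy the investigator and sponsor decide case by case. Subjects who miss doses are counseled (9.3), and poor compliance affects the per-protocol set, not attendance (12.8.1). Someone who stops applying but keeps attending is assessed at Week 6. An IGA is also due at ET. What stands is narrower: after exit, no efficacy assessment is scheduled.

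The second objection concerns the imputation. Each leaver's own earlier scores enter the model, so a subject doing badly is not filled in at the arm average. An example in which every input is assumed: Week 6 IGA normal with SD 1 and 23.6% below 1.5, so mean 1.5 + 0.72 = 2.22; Week 2 mean 2.6, SD 0.8; correlation 0.6. For a Week 2 score of 3, the Week 6 mean is 2.22 + 0.6 × (1/0.8) × 0.4 = 2.52 and the SD is 0.8. The chance of falling below 1.5 is about 10%. If all active leavers were like this and truly succeeded at 6.3%, 20% stopping would overstate the active rate by 0.2 × 3.7 = 0.7 points. This is why the table above is an upper-end case. It does not remove the problem, because earlier scores were mostly recorded on drug and cannot show what happens after stopping.

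Third, 23.6% is not a pure on-treatment rate. Section 12.8.2 says the estimates are "based on the LOCF method of handling missing values while the proposed Phase 3 analysis will account for missing values using multiple imputations", so they already carry dropouts' last values.

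Fourth, sensitivity analyses are planned. They help, but none observes the missing outcome: LOCF carries forward the last on-therapy score, GEE uses what was collected, and the tipping point analysis is unspecified.

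**Conclusion.** The concern holds in this form: no efficacy assessment is provided after early exit, the ITT set keeps early leavers, and their Week 6 IGA is imputed by a model with no term for stopping drug. The statement in 12.8.3 that the method does not rely on missing at random is wrong for standard MCMC imputation.

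The size is unknown. An overstatement of 0.9 to 3.5 points in the active rate, against a planned difference of 17.3, is an upper-end illustration. It rests on assumed stopping of 5% to 20%, imputation at 23.6%, true success at 6.3% and no bias in the vehicle arm. Vehicle stopping could offset or change it. A reader might infer that the trial's power is in danger. The figures do not support that: power is 94.7% or higher in every scenario above. The issue is bias and interpretability of the estimate. It deserves action because the remedy is cheap.

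**What to change.** In Sections 8.3 and 11.1.3:
- Separate stopping study drug from withdrawing from the study. Leave the existing pregnancy discontinuation rule unchanged.
- Ask subjects who stop early and are willing to attend the existing Week 6 and Week 10 visits for IGA, EASI, pruritus, adverse events and concomitant therapy.
- Record the date study drug stopped.

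In Section 12.8.3 and the SAP, before unblinding:
- Use the observed Week 6 IGA in the ITT analysis.
- State how a Week 6 IGA after prohibited AD therapy is scored. The plan has no such ITT rule: Section 9.4.1 records a deviation and 12.8.1 removes the subject from the per-protocol set.
- State that an ET IGA taken outside the Week 6 window is entered at the visit nearest its actual date, not as Week 6. That window is −3/+5 days in Table 1 and ±3 days in Section 12.8.6, so these must be reconciled first.
- Correct the statement on missing at random.

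The cost is a protocol amendment, one eCRF date and a few extra attendances at visits that already exist. Some subjects will decline or be lost and will still need imputation, so the problem shrinks but does not vanish.
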